## 1.2 Study objectives and endpoints

**Table 1 - Objectives and related endpoints**

	Objectives	Endpoints
Primary	
 
Evaluate organ absorbed radiation doses from PRRT with Lutathera in adolescent patients with SSTR-positive GEP-NETs and PPGLs as a pooled cohort
 
Evaluate safety and tolerability of Lutathera in adolescents with SSTR-positive GEP-NETs and PPGLs as a pooled cohort
 
	
 
Target organ (e.g. kidney and bone marrow) absorbed radiation doses in adolescents with SSTR-positive GEP-NETs and PPGLs as a pooled cohort
 
The incidence of adverse events (AEs) and laboratory toxicities after the 1st Lutathera administration in adolescents with SSTR-positive GEP-NETs and PPGLs as a pooled cohort
 

Secondary	
 
Evaluate cumulative safety of Lutathera in adolescents with SSTR-positive GEP-NETs and PPGLs as a pooled cohort
 
Evaluate long-term safety of Lutathera in adolescents with SSTR-positive GEP-NETs and PPGLs as a pooled cohort
 
Perform comparative assessment of dosimetry and pharmacokinetics (PK) between adolescent patients with GEP-NETs and PPGLs as a pooled cohort and adult patients using the extrapolation model developed for the clinical study
 
	
 
The incidence of adverse events (AEs) and laboratory toxicities until 6 months after the last Lutathera dose (short-term follow-up) in adolescents with SSTR-positive GEP-NETs and PPGLs as a pooled cohort
 
The incidence of adverse events (AEs) and laboratory abnormalities during the long term follow-up of 5 years after the last Lutathera dose in adolescents with SSTR-positive GEP-NETs and PPGLs as a pooled cohort Calculated organ absorbed doses and PK parameters based on imaging/blood radioactivity concentration data from adolescent with SSTR-positive GEP-NETs and PPGLs as a pooled cohort patients compared to the predicted distribution / organ absorbed doses
 

Final

Final

## **2 Statistical methods**

### **2.1 Data analysis general information**

The final analysis will be performed by Novartis/AAA and/or a designated clinical research organization (CRO). SAS version 9.4 or later will be used to perform all data analyses and to generate tables, figures and listings unless otherwise specified.

#### **General analysis conventions**

**Pooling of centers:** Unless specified otherwise, data from all study centers will be pooled for the analysis. Due to expected small number of patients enrolled at each center, no center effect will be assessed.

**Qualitative data** (e.g., gender, race, etc.) will be summarized by means of contingency tables; a missing category will be included as applicable. Percentages will be calculated using the number of patients in the relevant population or subgroup as the denominator.

**Quantitative data** (e.g., age, body weight, etc.) will be summarized by appropriate descriptive statistics (i.e. mean, standard deviation, median, minimum, and maximum).

#### **2.1.1 General definitions**

##### **Study drug**

Study drug will refer to Lutathera® (lutetium Lu 177 dotatate/ lutetium (177Lu) oxodotreotide ).

### **Study treatment**

Study treatment will refer to Lutathera® (lutetium Lu 177 dotatate/ lutetium (177Lu) oxodotreotide ) plus 2.5% Lys-Arg amino acid solution.

### **Date of first administration of study treatment**

The date of first administration of study treatment is derived as the first date when a nonzero dose of study treatment was administered as per the Study Drug Administration CRF. The date of first administration of study treatment will also be referred as *start of study treatment*.

### **Date of last administration of study treatment**

The date of last administration of study treatment is defined as the last date when a nonzero dose of study treatment was administered as per Dose Administration eCRF.

### **First cycle**

The first cycle is from date of first study treatment administration up to 56 days after date of first administration, the day before the next administration or the day of study discontinuation, whichever comes first.

### **Study day**

The study day describes the day of the event or assessment date relative to the reference start date.

The study day is defined as:

- The date of the event (visit date, onset date of an event, assessment date etc.) – reference start date + 1 if event is on or after the reference start date;
- The date of the event (visit date, onset date of an event, assessment date etc.) – reference start date if event precedes the reference start date.

The reference date for all assessments (safety, efficacy, dosimetry, etc) is the date of first administration of study treatment as defined above.

### **Time unit**

A year length is defined as 365.25 days. A month length is 30.4375 days (365.25/12). If duration is reported in months, duration in days will be divided by 30.4375. If duration is reported in years, duration in days will be divided by 365.25.

### **Baseline**

For safety and efficacy evaluations, the last available assessment on or before the date of first administration of study treatment is defined as the “baseline” assessment.

If patients have no value as defined above, the baseline result will be missing.

Final

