#### **8.4.5 ECG**

Standard 12-lead ECGs will be performed at screening (baseline), immediately after each Lutathera/amino acid treatment procedure (following the completion of the amino acids infusion), and at the EoT visit ([Table 8-2](#)) to measure the ECG intervals (RR, PR, QRS, QT and QTcF).

ECGs will be performed in triplicate (at least 5 minutes apart) after the patient has been in a sitting or supine position for at least 10 minutes, and not immediately after a meal. The parameters will be measured as a mean value of minimally 3 beats; the mean of each parameter has to be used for CRF completion. The preferred sequence of cardiovascular data collection at the timepoints with multiple assessments is ECG collection first, followed by vital signs, and blood sampling.

Additional, unscheduled, safety ECGs may be repeated at the discretion of the investigator at any time during the study as clinically indicated. Unscheduled ECGs with clinically significant findings should be collected in triplicate.

The Investigator will note in the source documents (and in the eCRF) whether the ECG is normal or abnormal, as well as the clinical relevance of abnormal ECGs results and the different ECG intervals measurements, calculated using the mean value of 3 measurements for each parameter. Relevant ECG abnormalities at screening will be recorded in the medical history page, while changes during the study will be recorded on the Adverse Event page of the eCRF.

The original ECGs on non-heat-sensitive paper or a certified copy on non-heat sensitive paper, appropriately signed, must be collected and archived at the study site. Each ECG tracing should be labeled with the study number, subject initials (where regulations permit), subject number, subject date of birth, ECG date, and kept in the source documents at the study site.

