**Figure 1-1 - Study design**

During the screening period of up to 2 weeks, participant eligibility will be determined according to the protocol's pre-defined inclusion and exclusion criteria. All screening assessments should be performed according to Table 8-2 of the protocol.

Participants who meet all eligibility criteria at screening can be enrolled in the study. The enrollment and Lutathera order must be performed immediately after all eligibility criteria are verified and the participant is confirmed to be eligible.

There will be no study visits after screening and before the 1st Lutathera administration. Somatostatin receptor imaging (SRI) performed before the screening (within 3 months prior to enrollment) can be used for the assessment of participant eligibility. Laboratory tests completed before the screening can be used for the assessment of participant eligibility if performed within 2 weeks prior to enrollment.

The treatment period will consist of 4 Lutathera treatments administered at  $8 \pm 1$  week intervals. Lutathera administration will occur on Week 1 Day 1 of each cycle. Each participant will receive a total of 4 doses of Lutathera (7.4 GBq/200 mCi  $\times$  4 administrations every 8 weeks; cumulative dose: 29.6 GBq/800 mCi).

An infusion of 2.5% Lysine - Arginine amino acid (AA) solution will be co-administered with each Lutathera dose for renal protection according to the approved Lutathera local prescribing information. An antiemetic will be administered for prevention of infusion-related nausea and vomiting.

For dosimetry assessments, SPECT/CT and whole Body images, urine and blood samples will be collected during the first week of the 1st Lutathera cycle as per Table 8-2 and Table 8-3 of the protocol, i.e. once during the study treatment period for each participant. The calculation of organ absorbed radiation dose, or dosimetry, after the 1st Lutathera administration will allow for estimation of the cumulative absorbed radiation dose from 4 Lutathera doses and for decision making on the next dose levels. In the exceptional circumstances when dosimetry cannot be performed in a particular participant after the first Lutathera dose, it should be completed as soon as feasible upon a later dose.

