### On-treatment assessment/event and observation periods

For adverse event reporting, the overall observation period will be divided into three mutually exclusive segments:

1. **Screening period:** from day of patient's informed consent to the day before first administration of study treatment
2. **on-treatment period:** from date of first administration of study treatment to 56 days (i.e. 8 weeks) after date of last actual administration of study treatment (including start and stop date).
3. **short-term follow-up period:** from day 57 after last administration of study treatment to day 183 (6 months) after date of last administration of study treatment
4. **long-term follow-up period:** starting from day 184 after last administration of study treatment

Safety summaries (tables, figures) include data from either on-treatment, short-term and long-term follow-up periods cumulatively with the exception of selection period data or baseline data which will also be summarized where appropriate. In particular, summary tables for adverse events (AEs) will summarize only on-treatment events, with a start date during the on-treatment period (**treatment-emergent** AEs) and specific listings of related SAEs and adverse events of special interest (AESI) will be provided for the short-term and long-term follow-up periods.

However, all safety data (including those from the short-term and long-term follow-up periods) will be listed and those collected during the short-term and long-term follow-up periods will be flagged.

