## 2.6.5 Other safety data

### 2.6.5.1 ECG and cardiac imaging data

12-lead ECGs including PR, QRS, QT, QTcF, and RR intervals will be obtained for each participant during the study. ECGs are reviewed locally by each investigative site and assessed centrally.

The summaries will include all on-treatment assessments available no later than 56 days after the last study treatment administration date (see Section 2.1.1).

The following summaries will be presented:

- Change from baseline for ECG parameters by timepoint.
- Number and percentage of patients with on-treatment notable ECG values.
  - QT or QTcF
    - New value of > 450 and ≤ 480 ms
    - New value of > 480 and ≤ 500 ms
    - New value of > 500 ms
    - Increase from baseline of > 30 ms to ≤ 60 ms
    - Increase from baseline of > 60 ms
  - HR (=60/RR in seconds)
    - Increase from baseline >25% and to a new HR > 100 bpm
    - Decrease from baseline >25% and to a new HR < 50 bpm
  - PR
    - Increase from baseline >25% and to a new PR > 200 ms
    - New PR > 200 ms
  - QRS
    - Increase from baseline >25% and to a new QRS > 120 ms
    - New QRS > 120 ms

ECG parameters will be listed, and periods of assessment will be flagged.

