## 4 Change to protocol specified analyses

No change from protocol specified analysis was made.

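### The SAP's date-only baseline rule makes the post-infusion Cycle 1 Day 1 ECG the ECG baseline, although the protocol names the screening ECG

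*SAP*

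**What the plan says.** SAP 2.1.1 (Baseline) gives one rule for safety and efficacy evaluations: "the last available assessment on or before the date of first administration of study treatment is defined as the" baseline value. The same section derives the first-administration date as a calendar date, with no clock time.

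Protocol 8.4.5 fixes the ECG timing. "Standard 12-lead ECGs will be performed at screening (baseline"), then "immediately after each Lutathera/amino acid treatment procedure (following the completion of the amino acids infusion"), and at the end-of-treatment (EoT) visit. Protocol 8.2 also lists ECG among the baseline data collected at screening.

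SAP 1.1 says of the interval between the two ECGs: "There will be no study visits after screening and before the 1st Lutathera administration".

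SAP 2.6.5.1 has no baseline rule of its own for ECG. It plans "Change from baseline for ECG parameters by timepoint" and "Number and percentage of patients with on-treatment notable ECG values". The notable values include QT or QTcF increases above 30 ms and above 60 ms, and changes of more than 25% in heart rate, PR and QRS.

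The SAP's on-treatment period runs "from date of first administration of study treatment to 56 days (i.e. 8 weeks) after date of last actual administration of study treatment", so it includes the first dosing day. SAP section 4 declares: "No change from protocol specified analysis was made".

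**The concern.** The protocol places the dosing-day ECGs straight after infusion, when an acute effect of Lutathera or the amino acids would be visible. Protocol 10.1.5 treats clinically significant ECG changes close to administration as events of special interest, and Protocol 12.5.2 calls for a categorical QT/QTc analysis that includes change from baseline.

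If the first post-infusion ECG is itself the baseline, that analysis compares post-infusion values with a post-infusion value. An acute effect common to all cycles cannot appear in it. The same record would also be both baseline and on-treatment. Because the SAP declares no departure from the protocol, this is an unreconciled conflict and not a stated choice.

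The problem is confined to ECG. Scheduled vital signs (Protocol 8.4.3) and Day 1 safety biomarkers (Table 8-2, footnote 13) are taken before dosing. Blood pressure and pulse would be exposed only if readings taken during or after the first infusion are entered in the database.

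**Working it through.** **1. Which ECG the rule selects.** Two scheduled ECGs fall on or before the first-dose date: screening, and Cycle 1 Day 1 after the amino acid infusion. That infusion lasts 4 hours, at most 6 (Protocol 6.7), so the Day 1 ECG normally carries the dosing date. It is the later of the two and the rule takes it. Screening is used only if the Day 1 ECG is missing or dated later. The advice to record ECG before vital signs and blood samples orders assessments within one timepoint; it does not move the Day 1 ECG before the dose.

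**2. What that does to the changes.** Let *d* be a constant acute post-infusion shift, absent at screening and EoT.

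| Timepoint | Screening baseline | SAP rule |
|---|---|---|
| Cycle 1 | *d* | 0 (subtracted from itself) |
| Cycles 2–4 | *d* | *d* − *d* = 0 |
| EoT | 0 | −*d* |

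For example, with *d* = 35 ms every post-infusion ECG belongs in the category above 30 and up to 60 ms. Under the SAP rule none is counted there and EoT shows −35 ms. With *d* = 65 ms the category above 60 ms is likewise empty and EoT shows −65 ms. One of the five scheduled post-baseline changes (four post-infusion plus EoT) is lost, and it is the only one in Cycle 1.

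**3. Size once measurement noise is added.** The plan gives no figure to reproduce and no ECG variability, so these inputs are assumptions: independent normal errors, SD *s* = 10 or 15 ms per recorded ECG value, and *d* = 0, 5, 10 or 20 ms. A difference of two ECGs has SD *s*√2, which is 14.1 or 21.2 ms.

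For one later post-infusion ECG with the screening baseline, P(increase > 30 ms) = 1 − Φ((30 − *d*)/(*s*√2)). At *d* = 10 this is 1 − Φ(20/14.1) = 0.079 and 1 − Φ(20/21.2) = 0.173. Under the SAP rule *d* drops out, leaving 1 − Φ(30/14.1) = 0.017 and 1 − Φ(30/21.2) = 0.079 whatever the shift.

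| *d* (ms) | Screening baseline | SAP rule |
|---|---|---|
| 0 | 0.017–0.079 | 0.017–0.079 |
| 5 | 0.039–0.119 | 0.017–0.079 |
| 10 | 0.079–0.173 | 0.017–0.079 |
| 20 | 0.240–0.319 | 0.017–0.079 |

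**4. Per patient.** The table below counts a patient with any post-infusion increase above 30 ms, by simulation with 1,000,000 draws. Cycles 1–4 are compared with screening, or Cycles 2–4 with Cycle 1 Day 1. Expected counts are the probability times 8.

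| *d* (ms) | Screening: probability | Expected of 8 | SAP rule: probability | Expected of 8 |
|---|---|---|---|---|
| 0 | 0.055–0.212 | 0.4–1.7 | 0.044–0.177 | 0.4–1.4 |
| 5 | 0.115–0.298 | 0.9–2.4 | 0.044–0.177 | 0.4–1.4 |
| 10 | 0.211–0.399 | 1.7–3.2 | 0.044–0.177 | 0.4–1.4 |
| 20 | 0.507–0.614 | 4.1–4.9 | 0.044–0.177 | 0.4–1.4 |

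**5. EoT.** The error there has the opposite sign. If the infusion shortened QTcF by 10 ms, the chance of a false increase above 30 ms at EoT would be 0.079–0.173 under the SAP rule, against 0.017–0.079 with the screening baseline.

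**The case against.** The strongest reply is that the intended ECG baseline is already written down. Protocol 8.4.5 and 8.2 both place it at screening, and the SAP says that it follows the protocol without change. On that reading the generic sentence was never meant to override the protocol, and a careful programmer would use screening. That is possible, but the SAP sentence governs the derivation, covers all safety evaluations and has no exception for ECG. The outcome should not depend on which document the programmer follows.

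Other objections limit the consequence, and they stand:

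- With no acute shift there is no systematic bias, only the loss of the Cycle 1 change. The documents give no shift in either direction.
- The probabilities depend on the assumed SD. Protocol 8.4.5 records the mean of triplicate ECGs. If that brought the SD to 5–7 ms, the single-ECG chance at *d* = 10 would be 0.2–2.2% instead of 8–17%. The cancellation of *d* does not depend on the SD.
- The per-patient counts cover post-infusion ECGs only. Including EoT at *d* = 0 gives 0.5–1.9 against 0.4–1.7. Eight is also a minimum: 11 patients had been enrolled by Amendment 03.
- The Day 1 ECG stays in the listings and in the absolute-value categories. An effect that grows over cycles remains partly visible.
- ECG is outside the primary endpoints, no hypothesis is tested, and investigators judge each ECG for clinical relevance.

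**Conclusion.** The concern holds. Read as written, the SAP makes a post-infusion, on-treatment ECG the baseline, contradicts Protocol 8.4.5, and contains nothing that overrides the rule for ECG. The Cycle 1 change is always zero. A constant acute effect of any size disappears from the Cycle 2–4 changes and appears reversed at EoT. The change-from-baseline table and the baseline-dependent QT/QTcF, heart rate, PR and QRS categories would therefore misstate any acute effect.

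These structural results need only the protocol schedule and a shift that is constant over cycles. The numerical size also rests on the assumed SD and shift: at 10 ms and an SD of 10–15 ms, 1.7–3.2 expected patients of 8 would fall to 0.4–1.4. Absolute cut-offs such as QTcF above 500 ms are exposed only if the undefined word *new* means absent at baseline. Raw values, listings and investigator-reported events are unaffected. This should be fixed, but it does not threaten the primary objectives.

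**What to change.** In SAP 2.1.1, define baseline as the last non-missing assessment before the start date and time of the first infusion, amino acid or Lutathera, whichever comes first. Add that a Day 1 assessment without a recorded time counts as baseline only where the protocol schedules it before dosing. This avoids relying on clock times that may not have been collected.

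For ECG, state in SAP 2.6.5.1 that baseline is the screening ECG (triplicate mean) and that the Cycle 1 Day 1 ECG is post-baseline. This statement alone removes the contradiction; the general rule guards against the same problem with any infusion-day vital signs that reach the database. In the same section, define *new* as not present at that baseline.

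The cost is one or two sentences and a programming condition, with no new data. The SAP also governs the final analysis, so the correction is useful even where earlier outputs have already been produced.

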### On-treatment assessment/event and observation periods

For adverse event reporting, the overall observation period will be divided into three mutually exclusive segments:

1. **Screening period:** from day of patient's informed consent to the day before first administration of study treatment
2. **on-treatment period:** from date of first administration of study treatment to 56 days (i.e. 8 weeks) after date of last actual administration of study treatment (including start and stop date).
3. **short-term follow-up period:** from day 57 after last administration of study treatment to day 183 (6 months) after date of last administration of study treatment
4. **long-term follow-up period:** starting from day 184 after last administration of study treatment

Safety summaries (tables, figures) include data from either on-treatment, short-term and long-term follow-up periods cumulatively with the exception of selection period data or baseline data which will also be summarized where appropriate. In particular, summary tables for adverse events (AEs) will summarize only on-treatment events, with a start date during the on-treatment period (**treatment-emergent** AEs) and specific listings of related SAEs and adverse events of special interest (AESI) will be provided for the short-term and long-term follow-up periods.

However, all safety data (including those from the short-term and long-term follow-up periods) will be listed and those collected during the short-term and long-term follow-up periods will be flagged.

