## 8 Visit schedule and assessments

Participants should be seen for all visits/assessments as outlined in the assessment schedule ([Table 8-2](#)). All data obtained from these assessments must be supported in the participant's source documentation. Missed or rescheduled visits will not lead to automatic discontinuation.

The screening period must be shortened as much as possible in order to enroll and treat the patients shortly after the informed consent signature. As Lutathera production and shipment will take approximately 12 days, Lutathera first dose must be ordered immediately after confirming patient eligibility and enrollment. There will be no study visits after screening and before the 1st Lutathera administration.

The treatment period consists of 4 treatment cycles, with Lutathera administration on Week 1 Day 1 of each cycle. The dosimetry assessments will be performed during the first week after the 1st Lutathera dose as per [Table 8-2](#) and [Table 8-3](#). In the exceptional circumstances when dosimetry cannot be done in a particular patient after the first dose, it should be done as soon as feasible upon a later dose. Patients might need to stay overnight at the hospital or another facility for the days with intensive assessments (e.g. for Lutathera administration, blood sampling and imaging). The decision on the overnight stay is up to Investigator, as appropriate according to medical judgment, local regulation and patient's preference.

The End of Treatment (EoT) visit should be performed in 8 weeks after the last Lutathera administration for patients who complete all 4 Lutathera doses (end of Cycle 4). Participants who prematurely discontinue the study treatment for any reason should be scheduled for the EoT/Early Termination visit as soon as possible, at which time all of the assessments listed for the EoT visit will be performed (refer to "*EoT or early termination*" column in [Table 8-2](#)). At this EoT visit, all adverse events and concomitant medications taken during the Treatment period should be reconciled and recorded on the eCRF.

During the short-term follow-up, visits will occur every 6 weeks until 6 months after the last Lutathera dose, and during the long-term follow-up visit will occur every 6 months until 5 years after the last Lutathera dose. The last follow-up visit (5 years after the last dose of Lutathera) will be considered as End of Study (EoS) visit for each patient.

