|                       |                  | 12. Blood collection for dosimetry includes 6 radioactive blood samples at the following time points: before the start of Lutathera infusion, at the end of Lutathera infusion, then at 2h, 6h, 24h and 72h after the end of Lutathera infusion.
13. On Day 1 of Cycle 1, safety biomarkers are assessed pre-dose.
14. Safety biomarkers are taken either at Week 7 of cycle 1 or pre-dose of cycle 2.
15. Safety Biomarkers are taken either at Week 7 of cycle 4 or at the EoT visit.
S = assessment to be recorded in the source documentation only and not recorded in CRF page.
* The last FU visit would be the EOS visit for patients who completed the long-term FU period; and a separate EOS visit should be planned for patients who discontinued from the study prior to completion of the long-term FU period. |                |               |         |               |         |         |            |         |         |  |                          |                          |                          |  |

Variations of  $\pm$  1 week are allowed for the visits during the Treatment period (including the window for Lutathera administration visits that should occur in 8 weeks from the previous dose  $\pm$  1 week), and during the Short-term Follow-up. The exception is the week when dosimetry assessments are performed – during the dosimetry week, all visits must occur on the Days specified in the [Table 8-2](#).

During the Long-term Follow-up, a visit window of  $\pm$  1 month is allowed.

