### **12.5.2 Safety endpoints**

For all safety analyses, the FAS will be used. All listings and tables will be presented for all GEP-NET and PPGL participants as a pooled cohort.

Safety summaries (tables, figures) include only data from the on-treatment period with the exception of baseline data which will also be summarized where appropriate (e.g. change from baseline summaries) and long-term safety assessments which will be summarized separately. In addition, a separate summary for death including on treatment and post treatment deaths will

be provided. In particular, summary tables for adverse events (AEs) will summarize only on-treatment events, with a start date during the on-treatment period (treatment-emergent AEs).

The on-treatment period lasts from the date of first administration of study treatment to 56 days after the date of the last actual administration of Lutathera.

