Interim analyses will be performed to evaluate dosimetry and safety when at least five patients (including at least two GEP-NET patients) have completed at least one cycle of treatment. The data from all completed treatment cycles will be presented. The interim analyses will be of a descriptive nature, and no statistical hypotheses will be tested.

The primary analysis to address the primary objective will be performed after at least 8 patients (including at least 3 GEP-NET patients) have completed the first cycle (up to cycle 2 pre-dose assessments) at which time both dosimetry and safety assessments of the first cycle will have been completed for all participants. In case the last participant has dosimetry assessments after the 2nd or a later dose, the data cut-off will be performed after that dose (and before the subsequent cycle pre-dose assessments). The primary analysis in the study will be of descriptive nature and no statistical hypothesis will be tested. All data available at that time from pooled cohorts will be used for the assessment of the primary and secondary objectives. [REDACTED]

[figure not shown]
A final analysis will be performed after all subjects who have received at least one dose of Lutathera have completed the 5 years follow-up or have withdrawn from the study.

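### The on-treatment cut-off for assessments falls on the nominal End of Treatment day, so an EoT ECG done up to a week late enters no ECG summary

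*SAP*

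**What the plan says.** **Analysis window.** SAP 2.1.1 ends the on-treatment period "to 56 days (i.e. 8 weeks) after date of last actual administration of study treatment", last day included. Short-term follow-up then runs "from day 57 after last administration of study treatment to day 183 (6 months"). Protocol 12.5.2 agrees: the period lasts "to 56 days after the date of the last actual administration of Lutathera".

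**Visit timing.** Protocol section 8: "The End of Treatment (EoT) visit should be performed in 8 weeks after the last Lutathera administration" for patients who receive all four doses, and the same sentence places that visit at the end of Cycle 4. The notes under Table 8-2 say that variations of plus or minus 1 "week are allowed for the visits during the Treatment period" and in short-term follow-up. For patients who stop early, section 8 asks for the EoT/early-termination visit as soon as possible, with no fixed day.

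**Summaries.** SAP 2.6.5.1 limits the ECG summaries to on-treatment assessments "available no later than 56 days after the last study treatment administration date". SAP 2.6.4 (laboratory, including safety biomarkers) and 2.6.5.2 (vital signs) set the same limit, but each adds separate summaries that include follow-up data. Section 2.6.5.1 adds none. SAP 2.1.1 states that all safety data will be listed, with follow-up data flagged.

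**The concern.** The analysis window has no tolerance where the visit schedule has a week. One patient attends on day 56 and another on day 58. Both comply, yet only the first contributes an EoT result to the on-treatment tables. No rule moves the second back: the SAP's remark on visit windowing concerns unscheduled visits only.

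The EoT assessment shows the state of the patient after the full course. For ECG it also has a particular role. Protocol 8.4.5 schedules ECGs at screening, straight after each infusion procedure, and at EoT. EoT is therefore the last scheduled ECG and the only post-baseline one not taken right after an infusion. Cardiovascular disorders are among the adverse events of special interest in Protocol 10.1.5. With about eight patients, one absent result matters: 1/8 = 12.5 percentage points.

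Safety biomarkers are exposed in a milder way. By the footnotes to Table 8-2, the treatment-phase draws are before dose 1, then at Week 7 of cycle 1 or before dose 2, then at Week 7 of cycle 4 or at EoT. If the last draw is a late EoT, the on-treatment worst value omits the only treatment-phase sample after dose 4 and rests on one taken after a single dose. Table 8-1 names all four cycles and both follow-up periods without time points, so this rests on Table 8-2.

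**Working it through.** **1. The plan's figure.** 8 weeks × 7 = 56 days. The SAP's equation of 56 days with 8 weeks is reproduced, and the cut-off is exactly the nominal EoT day.

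**2. Permitted EoT days, if the one-week allowance applies.** 56 − 7 = 49 and 56 + 7 = 63, so days 49 to 63, which is 15 days. Days 57 to 63, which is 7 days, lie beyond the cut-off: 7/15 = 46.7%.

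**3. Where a late EoT result appears.**

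| Data | On-treatment table | Summary including follow-up | Listing |
|---|---|---|---|
| ECG (SAP 2.6.5.1) | no | none planned | yes |
| Laboratory, safety biomarkers (SAP 2.6.4) | no | yes | yes |
| Vital signs (SAP 2.6.5.2) | no | yes | yes |

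The liver-function table in SAP 2.6.4 uses worst post-baseline values, and its subsection states no day-56 limit.

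**4. Number of patients.** The share q of late EoT visits is an assumption, because the documents give no distribution. Expected number affected = n × q; chance of at least one = 1 − (1 − q)^n, treating patients as independent. The values of n are 8 (the planned minimum) and 11 (enrolled by 14 December 2023, from the Amendment 03 section).

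| q | n = 8: expected | n = 8: at least one | n = 11: expected | n = 11: at least one |
|---|---|---|---|---|
| 10% | 0.8 | 1 − 0.9^8 = 57% | 1.1 | 69% |
| 25% | 2.0 | 1 − 0.75^8 = 90% | 2.8 | 96% |
| 46.7% | 3.7 | 1 − (8/15)^8 = 99% | 5.1 | 99.9% |

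The last row is what evenly spread visit dates would give. It is an illustration, not a forecast.

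**5. Would a longer fixed cut-off do?** A day-63 limit would capture every in-window EoT and would not meet the Week 13 visit, whose earliest day is 13 × 7 − 7 = 84. It would not capture all early-termination visits. Protocol 6.5.1.1 ties discontinuation to a delay beyond 16 weeks from the intended next dose, so such a visit could come about 8 + 16 = 24 weeks, or 168 days, after the last dose. Assignment by visit label covers both cases.

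**The case against.** **The cut-off is deliberate and consistent.** Protocol and SAP agree on it. It equals the dosing interval and matches the 56 days used for exposure duration, concomitant medication and end-date imputation. This stands. It is a reason to leave the adverse-event window alone, but it does not explain why a scheduled assessment should change period because of a permitted delay.

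**The one-week allowance may not cover EoT.** Table 8-2 gives EoT its own column, and the allowance names the treatment period and short-term follow-up. Section 8 puts EoT at the end of Cycle 4, so the allowance most naturally applies, but this is not stated word for word.

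**A programmer might keep a late EoT ECG anyway.** SAP 2.1.1 presents by-visit tables by scheduled visit and has a general sentence about summarising the periods cumulatively. Section 2.6.5.1, however, sets its own day limit and lacks the addition found in 2.6.4 and 2.6.5.2. Followed as written, it excludes the late ECG. The tension between the general and specific text is a further reason to settle it.

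**The damage is small.** Post-infusion ECGs are unaffected, so only the final ECG is exposed. This also stands.

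**The primary first-cycle tables.** A reader might infer that these suffer too, because the first cycle can end "the day before the next administration or the day of study discontinuation, whichever comes first" while the primary analysis waits until patients "have completed the first cycle (up to cycle 2 pre-dose assessments"). The documents do not support this. That is a separate rule, and the second phrase fixes when the analysis is run, not which values enter the tables. The first-cycle tables in SAP 2.5.2 cover adverse events, hematology and biochemistry. Protocol 8.4.6 places the cycle 1 post-dose samples at Weeks 3, 5 and 7, which normally lie inside the window. The routine laboratory rows of Table 8-2 are not legible in the available text, so a routine hematology or chemistry draw on the day of dose 2 cannot be shown.

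**Conclusion.** The point holds in a limited form. Under the natural reading of the visit allowance, a compliant EoT on days 57 to 63 falls outside the on-treatment assessment tables. For ECG this means no summary at all, only a listing. For laboratory, safety-biomarker and vital-sign data it means a move to the cumulative summaries.

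Two stronger inferences should be resisted. End-of-treatment data are not lost, since all are listed and most are also summarised elsewhere. Nor can it be said that about half the patients will be affected: that assumes evenly spread visit dates, which nothing in the documents supports. Over the range of 10% to 47% late, 0.8 to 3.7 of 8 patients are affected, with a 57% to 99% chance of at least one.

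The two documents do not contradict each other. The gap is between the analysis window and the visit window. The study is descriptive, so no test or error rate is involved. This is a worthwhile, inexpensive improvement and does not threaten the primary objective.

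**What to change.** In SAP 2.6.4, 2.6.5.1 and 2.6.5.2, state that assessments labelled as the scheduled EoT or early-termination visit count as on-treatment whatever day they fall on. Put matching wording in Protocol 12.5.2. Keep the 56-day window for adverse events, which is the purpose for which SAP 2.1.1 defines the periods, and leave the other uses of 56 days as they are. In listings, flag these assessments as on-treatment so that tables and listings agree.

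The cost is wording in three SAP sections and one protocol section, plus one assignment rule in programming. No new data are needed. The drawback is that some EoT results will come from later than 8 weeks: slightly later for most, considerably later after a long dose delay. Show the day of assessment relative to the last dose, or footnote those beyond day 56, so that a reader can judge them.
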